5.4. Other Efficacy Endpoints

Other efficacy endpoints include the overall MRD conversion rate at any time after randomization, durable MRD negativity rate, response rates including CR or better rate and sCR rate, OS, and duration of CR.

5.4.1. Definition

MRD by NGS are evaluated post-baseline at the end of 12, 18, 24, and 36 months after the start of study treatment(s). The overall MRD negativity (10^{-5}) conversion rate at any time after randomization is defined as the rate of MRD converted from positive at baseline to negativity at the threshold 10^{-5} achieved at any time after randomization.

In addition, MRD negativity (10^{-5}) conversion rate at 12, 18, 24 and 36-months landmark time with +/- 2 months window, as well as accumulative rate up to these timepoints will be summarized. MRD negativity (10^{-5}) CR conversion rates for FAS patients, and MRD negativity (10^{-5}) conversion rates for those achieved CR or better response per computerized algorithm will be summarized in a similar manner.

Durable MRD (≥ 1 year) negativity rate, defined as the proportion of subjects who have achieved MRD negative status (at 10⁻⁵) in 2 bone marrow aspirate examinations that are a minimum of 1 year apart, without any examination showing MRD positive status in between assessments. Subjects who have achieved MRD negative status on or after PD or switch to subsequent antimyeloma therapy before PD, will not be considered MRD negative. Subjects with missing or unevaluable MRD status will be considered as MRD positive.

Similar analysis will be performed for durable MRD (≥6 months) negativity rate.

OS, measured from the date of randomization to the date of the subject's death due to any cause. Subjects who died after consent withdrawal will be considered as having an OS event. Subjects who are lost to follow-up will be censored at the time of lost to follow-up. If the patient is alive and vital status is unknown, then the patient's data will be censored at the date the patient was last known to be alive determined by the maximum collection/assessment date from among selected data domains within the clinical database.

Response rates by IMWG 2016 criteria including CR or better rate and sCR rate, defined as the proportion of subjects who achieve the respective responses prior to the first subsequent antimyeloma therapy per computer algorithm in accordance with the IMWG criteria, during or after the study treatment. All subjects are assumed to be VGPR at baseline to enter the study per inclusion criteria. Subgroup analysis will be performed for CR or better rate per computer algorithm with forest plot provided. In addition, responses per investigator assessment by IMWG 2016 criteria will be summarized. Shift tables will be provided to summarize the best responses from baseline vs. post-baseline for each treatment group.

Duration of CR, calculated from the date of initial documentation of a response of CR or sCR at or after randomization to the date of first documented evidence of PD (as defined in the IMWG criteria), or death due to PD, whichever occurs first, for subjects who have CR or better as their best response. Subjects who have not progressed or who die due to causes other than disease progression will be censored at the last disease evaluation before the start of subsequent antimyeloma therapy. Subjects who achieved CR or sCR prior to randomization will use randomization date as their starting time of CR or sCR for calculating duration of CR.

Time to the first response of CR or better is defined as the time between randomization and the first efficacy evaluation at which the subjects meet all criteria for CR or better based on computerized algorithm, according to IMWG response criteria. For subjects who achieved CR or sCR prior to randomization, time to CR or better will be set as 0 day.

In addition to protocol specified other secondary efficacy endpoints, progression-free survival on next line of therapy (PFS2) and time to subsequent therapy will be evaluated.

PFS2 is defined as the time from randomization to progression on next line of therapy or death, whichever comes first. Disease progression on the next line of treatment will be based on investigator assessment. Any deaths are considered as PFS2 events. Subjects who start next line of therapy without disease progression on study treatment will be censored at the last disease assessment before starting next line of therapy. For subjects who start next line of therapy after progression on study treatment, are still alive and not yet progress on next line of therapy or progressed on or after a 2nd line of next therapy, they will be censored on minimum of the last date of follow-up and start date of 2nd line of next therapy minus 1. Subjects without any post-baseline follow-up will be censored at the randomization. Time to subsequent antimyeloma therapy is defined as the time from randomization to the start of subsequent antimyeloma treatment. Death due to PD without start of subsequent therapy will be considered as event. Subjects who withdrew consent to study or are lost to follow, or die due to causes other than disease progression will be censored at the date of death or the last date known to be alive.

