- 4. Have archived bone marrow samples collected before induction treatment (ie, at diagnosis) or before transplant (eg, at the end of induction) or have existing results on the index MM clone based on Adaptive Biotechnologies' NGS-based MRD assay. Archived bone marrow samples will be used for calibration of myeloma clonal cells to facilitate assessment of the primary endpoint by NGS. Any one of the following archived bone marrow samples are required:
 - Greater than 1 mL viable frozen bone marrow aspirated aliquot (preferred) collected in an ethylenediaminetetraacetic acid tube, and stored at a temperature of -80° C, or
 - Non-decalcified diagnostic bone marrow aspirate clot sections (block or slides) for MRD assessment:
 - A Formalin fixed paraffin embedded (FFPE) block of bone marrow aspirate clot, or slides (preferably 5 slides, if available), 5 µm each, of non-decalcified bone marrow, or
 - Slides (preferably 5 slides, if available), bone marrow aspirate smear.
 - Please note: bone marrow core sections are not acceptable samples for analysis.
 - In exceptional circumstances when index myeloma clone cannot be identified from the archived bone marrow sample, a post-transplant sample can be used to identify myeloma clone with permission from the Sponsor.
 - If an existing result on index myeloma clone is available from Adaptive Biotechnologies' NGS-based MRD assay, conducted as part of institutional procedures, then archived bone marrow sample is not required as long as Adaptive Biotechnologies is able to retrieve historical results on the index myeloma clone from the clinical database.
- 5. Have residual disease as defined by detectable MRD by NGS (Adaptive Biotechnologies' NGS-based MRD assay). If this assay was conducted post ASCT as part of institutional procedures and MRD results are available during screening, then patients who were MRD positive at 10⁻⁵ based on existing NGS test result are also eligible to participate in the study (such patients will NOT be required to undergo MRD assessment by NGS again at the time of screening),
- 6. Be anti-CD38 treatment naïve.

DOSAGE AND ADMINISTRATION

The 2 treatment arms comprise of daratumumab in combination with lenalidomide or lenalidomide alone as follows (each treatment cycle will be 28 days, with a maximum duration of maintenance treatment of 36 cycles):

- 1. Daratumumab 1800 mg administered by SC injection:
 - Weekly during C1 and C2,
 - Every 2 weeks during C3 to C6, and

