		deemed necessary by the investigator, patients may also be observed after subsequent injections.			 Administration Medications for patients treated with daratumumab Lenalidomide 10 mg PO: Days 1 to 28 (continuously) of each 28-day cycle until confirmed PD, unacceptable toxicity, or until end of study treatment. If a patient experiences toxicity to lenalidomide, dose and/or schedule may be modified per institutional standard. After 3 cycles of maintenance therapy, if well tolerated, the lenalidomide dose may be increased to 15 mg daily, at the discretion of the investigator. The start of each cycle may occur ±3 days of the schedule day to accommodate the schedule of the site or patient. Day 1 of subsequent cycles should be adjusted accordingly to maintain the intended cycle duration. Any delays ≥4 days of the schedule day will need to be discussed with the sponsor.

				STUDY PHA	SES/VISI	TS ^a	
	PROCEDURE		SCREENING	Maintenance (Cycles 1–36)	ЕОТ	Follow-up (from the date of last study treatment until the end of study)	NOTES
	PROs						
	EORTC QLQ-C30, EORT EQ-5D-5L	At C1D1, and at the end of 6, 12, 24, and 36 months of treatment, (ie, C1D1, C7D1, C13D1, C25D1 and EOT). PROs should be administered at specified timepoints even after patient discontinues the study treatment.		PROs must be completed prior to conducting any other study-specific procedures. PROs should be completed at EOT if the patient discontinues early.			
	DISEASE EVALUATIONS						
	LABORATORY EVALUATION	S (TESTS TO BE CONDUC	TED AT THE CEN	TRAL LABORATORY)			
	IMWG Response Evaluat Assessment	ion per Investigator	х	D1 of every 3 rd cycle (ie, every 3 months) beginning with C1D1, during the first Year (ie, C1D1, C3D1, C6D1, C9D1, C12D1), followed by every 6 th cycle (ie, C18D1, C24D1, C30D1, C36D1) during Year 2 and Year 3	х	Every 6 months	IWMG Response Assessments during the Follow-up visits will be done for participants who have completed study treatment (36 cycles) or who have prematurely discontinued study treatment (due to reasons other than progressive disease). These assessments are to be performed based on local efficacy laboratory results. Assessments can stop after confirmation of Progressive Disease by the investigator. Determination of progressive disease, as well as other response assessments are to follow the IMWG criteria for assessment of progressive disease and disease response, as outlined in Table 7.
	β2-microglobulin and LDI	Н	X	-	Х	-	-

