MRD (aspirate) by NGS	X (NGS)	At the end of 12, 18, 24, and 36 months (NGS), (ie, C13D1, C19D1, C25D1 and at the EOT visit)	X		 During Screening: NGS assay (Adaptive Biotechnologies' NGS-based MRD assay) to be done on bone marrow aspirate collected during screening to determine eligibility for study entry. Residual samples, if available, will also be banked for future tests. Two sequential NGS assays will be done during screening. The first NGS assay will be conducted on archived bone marrow samples for calibration and identification of the index myeloma clone. Obtain archived bone marrow samples as described in Inclusion Criterion #4. If an existing result on index myeloma clone is available from Adaptive Biotechnologies' NGS-based MRD assay, conducted as part of institutional procedures, then archived bone marrow sample is not required as long as Adaptive Biotechnologies is able to retrieve historical results on the index myeloma clone from the clinical database. Following index clone calibration (or verification of existing index clone results from a previously conducted Adaptive Biotechnologies' NGS-based MRD assay), MRD will be assessed by NGS (Adaptive Biotechnologies' NGS-based MRD assay), using fresh bone marrow aspirate sample collected during screening. Note: If Adaptive Biotechnologies ' NGS- based MRD assay was conducted post-ASCT as part of institutional procedures and MRD results are available at screening, these results are to be recorded in the eCRF. Patients who are MRD positive at 10⁻⁵ based on an existing post-ASCT NGS assay conducted by Adaptive Biotechnologies, are eligible to participate. Such patients will not be required to undergo NGS based MRD assessment again during screening. After the start of study treatment (after C1D1):
-----------------------	---------	--	---	--	---

		STUDY PHA			
PROCEDURE	SCREENING	Maintenance (Cycles 1–36)	ЕОТ	Follow-up (from the date of last study treatment until the end of study)	Notes
					 NGS is to be conducted at 12, 18, 24, and 36 months: During the bone marrow aspirate procedure, the first aspirate sample that is drawn will be sent to the central laboratory to determine MRD by NGS. All bone marrow aspirates to be sent to the central laboratory should be at least 3 mL. Additional bone marrow aspirate samples may be taken and used for local laboratory testing. Bone marrow aspirate collected within ±30 days of the scheduled visit during the maintenance phase is acceptable.

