17.9. Study Completion/Termination

17.9.1. Study Completion/End of Study

The end of the study is defined as 36 months from the date of randomization of last patient. If a patient has died, the date and cause of death will be collected and documented in the eCRF. Patients benefiting from treatment with daratumumab and/or lenalidomide may continue receiving treatment after the end of the study treatment period of 36 months and after the end of the study, per the investigator's discretion. However, because the study specified treatment is for 36 months, the sponsor will not provide daratumumab and/or lenalidomide after the end of the study, unless required by local health regulatory authorities. The final data from the study site will be sent to the sponsor (or designee) after completion of the final patient assessment at that study site, in the time frame specified in the Clinical Trial Agreement.

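### Read as ordinary months, the 24- and 36-month MRD landmark windows in SAP 5.4.1 open only about 2 days before the cycle-based visits they are meant to capture

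*SAP*

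**What the plan says.** **Cycle length and label.** The protocol synopsis (Dosage and Administration) states "each treatment cycle will be 28 days, with a maximum duration of maintenance treatment of 36 cycles". Protocol 17.9.1 calls the same treatment period 36 months: "because the study specified treatment is for 36 months". The response-evaluation row of the Time and Event Schedule, Part 1, likewise glosses every third cycle as "ie, every 3 months) beginning with C1D1, during the first Year".

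**MRD visits.** The MRD row of the same schedule places the samples "At the end of 12, 18, 24, and 36 months (NGS), (ie, C13D1, C19D1, C25D1 and at the EOT visit" and adds: "Bone marrow aspirate collected within ±30 days of the scheduled visit during the maintenance phase is acceptable". The EOT visit is a separate study phase, due 30 days (+/-7) after the last dose. Lenalidomide is planned for Days 1-28 of each cycle; Protocol 6.3.3 also allows a Day 1-21 schedule after toxicity.

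**Landmark analysis.** SAP 5.4.1 counts the MRD time points from the start of study treatment. In addition to the any-time rate, it summarises the "conversion rate at 12, 18, 24 and 36-months landmark time with +/- 2 months window" and the cumulative rate up to each time point. Neither SAP 5.4.1 nor any other SAP section gives the length of a month or links the landmarks to C13D1, C19D1, C25D1 and EOT.

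**The concern.** The samples are scheduled in 28-day units, while the windows that decide which samples count are written in months. A 28-day cycle is about 2.4 days shorter than an average month. The gap between label and visit therefore grows with time, until it has used up nearly all of the 2-month allowance on the early side. A window that looks generous becomes lopsided: almost no room for an early sample and about 4 months for a late one.

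At stake is which samples enter the landmark rates. A sample that the protocol accepts as the 24-month sample could be assigned to no landmark. Two programmers could also take different month conventions and report different 24- and 36-month rates from the same data.

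**Working it through.** **The plan's own figure.** 36 cycles x 28 days = 1008 days. At 365.25/12 = 30.4375 days per month, 1008/30.4375 = 33.1 months, not 36. The stated 36 months is recovered only with a 28-day month (1008/28 = 36).

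**Scheduled days after C1D1, no cycle delay.**
- C13D1 = 12 x 28 = 336; C19D1 = 18 x 28 = 504; C25D1 = 24 x 28 = 672.
- EOT after Day 1-28 lenalidomide: last dose C36D28 = 35 x 28 + 27 = 1007; plus 30 = 1037.
- EOT after Day 1-21 lenalidomide: last dose C36D21 = 35 x 28 + 20 = 1000; plus 30 = 1030.

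**Windows.** Lower limit = (landmark - 2) x 30.4375; upper limit = (landmark + 2) x 30.4375.

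| Landmark | Scheduled day | Months | Window (days) | Room on the early side |
|---|---|---|---|---|
| 12 | 336 | 11.04 | 304.4-426.1 | 31.6 days |
| 18 | 504 | 16.56 | 487.0-608.8 | 17.0 days |
| 24 | 672 | 22.08 | 669.6-791.4 | 2.4 days |
| 36, Day 1-28 | 1037 | 34.07 | 1034.9-1156.6 | 2.1 days |
| 36, Day 1-21 | 1030 | 33.84 | 1034.9-1156.6 | -4.9 days (outside) |

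The 18-month window closes at day 608.8 and the 24-month window opens at day 669.6. A sample taken for C25D1 on days 642-669 is within the protocol's 30 days but falls in neither window.

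**Share outside.** The documents give no sampling dates. I assume them uniform over whole days around the scheduled visit.
- 12 months, +/-30 days: none outside.
- 18 months, +/-30 days (474-534): days 474-486 are outside, 13/61 = 21%.
- 24 months, +/-30 days (642-702): days 642-669 are outside, 28/61 = 46%. With +/-7 days (665-679): 5/15 = 33%.
- 36 months, Day 1-28, +/-7 days (1030-1044): days 1030-1034 are outside, 5/15 = 33%. With +/-30 days, if that tolerance applied to EOT: 28/61 = 46%.
- 36 months, Day 1-21, +/-7 days (1023-1037): days 1023-1034 are outside, 12/15 = 80%.

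**Sensitivity at 24 and 36 months, Day 1-28 dosing, +/-30 days.**
- Cumulative cycle delay moves the visits later, into the window: 34% outside at 7 days' delay, 23% at 14, 11% at 21 and 0% at 28.
- With 30-day months and no delay, the windows open at days 660 and 1020: 18/61 = 30% at 24 months and 13/61 = 21% at 36 months. The Day 1-21 EOT (1030) is then inside.
- For Day 1-21 patients under 30.44-day months, 5 days of accumulated delay brings the scheduled EOT to day 1035, just inside.

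**The case against.** The best reply is that the plan uses month as shorthand for a 28-day cycle. The schedule maps the 12-, 18-, 24- and 36-month samples to cycle visits, equates three cycles with 3 months, and in the other-malignancy row equates 6 months with 24 weeks. On that reading the 24-month window is 672 +/- 56 days (616-728), which holds every sample on days 642-702. The 36-month window is 1008 +/- 56 days (952-1064), which holds EOT at 1037 +/- 7. SAP 2.1 also says that data collected by cycle are generally summarised by nominal cycle. This reading is possible, but the SAP does not state it for MRD. The examples in SAP 2.1 are laboratory, vital-sign and PRO data; the same section handles the 12-month MRD assessment with a window in months, and SAP 5.4.1 does so again for the landmarks.

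Several stronger readings are tempting, and the documents do not support them:

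- **That samples taken on schedule are lost.** Under standard dosing the exact scheduled day is inside every window, by about 2 days at 24 and 36 months. Only early samples, or EOT after Day 1-21 lenalidomide, fall out.
- **That nearly half the samples will be lost.** The 46% needs uniform sampling over the whole tolerance and no delay in 24 to 36 cycles. At 36 months it also applies a 30-day tolerance that the protocol states for the maintenance phase, while EOT has its own +/-7 days.
- **That landmark rates will be biased downwards.** Counting a missing MRD status as positive is stated for the primary endpoint (SAP 5.2.1) and for durable negativity (SAP 5.4.1), not for the landmark rates. SAP 5.1.2 plans no imputation for other efficacy endpoints.
- **That the arms will be affected differently.** No delay rates by arm are given, and Protocol 6.3.1 holds both drugs during a cycle delay.

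**Conclusion.** The point stands as a minor one. On the ordinary meaning of a month, the SAP's stated rule can drop samples that the protocol accepts, which is more than a missing detail. The size cannot be fixed from the documents. Under standard dosing it runs from 0% (28 days' cumulative delay) to about 46% (no delay, uniform +/-30-day sampling), with about 33% for +/-7 days and no delay. The Day 1-21 case at 36 months rests on 30.44-day months and less than 5 days of accumulated delay.

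The reach is narrow. The landmark rates are additional summaries, and SAP 5.1.1 treats all efficacy endpoints other than the primary and PFS as exploratory. A reader might infer a threat to the primary result, but there is none: SAP 5.2.1 takes any record from randomization to 12 + 2 months. The any-time rate and the cumulative rates also have no lower cut-off, so they keep early samples.

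**What to change.** In SAP 5.4.1, replace the month windows by windows in days around the scheduled visits, for example 336, 504, 672 and 1037 days after C1D1, each +/-60 days: 276-396, 444-564, 612-732 and 977-1097. These do not overlap. With no delay they contain every sample within 30 days of its visit, and also a Day 1-21 EOT at 1030 +/- 7 (1023-1037). State the month length and the time origin; under the study-day rule in SAP 2.5 the four targets are Study Days 337, 505, 673 and 1038.

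Alternatively, assign samples by nominal visit (C13D1, C19D1, C25D1, and EOT for patients who completed 36 cycles). That also covers cumulative delays of more than 30 days, where a sample taken 30 days late would pass the upper limit of a fixed +/-60-day window.

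The cost is a few lines of SAP text. No new data, visits or protocol changes are needed.

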3.2.6. Summary of Anticipated Benefits and Risks

The combination of lenalidomide with SC administration of daratumumab is anticipated to have a positive benefit-risk profile when used for maintenance treatment of patients with newly diagnosed multiple myeloma who are MRD positive and anti-CD38 antibody naïve. Please refer to Section 3.2.1 for additional information. This assessment is based on the following:

• Strategies directed at improving and/or maintaining depth of response are needed to improve clinical outcomes for patients with newly diagnosed multiple myeloma.

- The addition of daratumumab to the standard of care lenalidomide, which is the current a standard of care regimen for maintenance treatment in patients with newly diagnosed multiple myeloma, may improve long-term outcomes through improvement in MRD conversion rate.
- Given the potential advantages of SC administration of daratumumab (refer to Section 3.2.2.2 for detailed information), including shorter time of administration, fewer injection-related reactions, and comparable clinical response rates when compared with administration of daratumumab via IV infusion, the SC route of administration will be used in this study.
- The assessment of primary endpoint of MRD negativity at 12 months post-maintenance will be conducted using a sensitive NGS (sensitivity cutoff of 10⁻⁵) assay (Adaptive Biotechnologies' NGS-based MRD assay), thus providing valuable data on the depth of response achieved with the combination of daratumumab and lenalidomide maintenance treatment in newly diagnosed multiple myeloma patients.
- We expect that the benefits of addition of SC daratumumab to lenalidomide, as maintenance treatment, will outweigh the risks, even among patients who may achieve a CR or better after transplant. As discussed in Section 3.2.1, prolonged administration of daratumumab in conjunction with lenalidomide does not result in an increased total risk of AEs based on data from ongoing trials.
- The potential risks for the study will be mitigated by monitoring via the Independent Data Monitoring Committee and the sponsor's medical monitor during the conduct of the study.

In summary, there is a strong rationale for evaluating SC daratumumab in combination with lenalidomide as maintenance treatment for patients with newly diagnosed multiple myeloma who are anti-CD38 naïve and MRD positive after frontline ASCT.

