4.1. Inclusion Criteria

Each potential patient must satisfy all of the following criteria to be enrolled in the study. Each patient:

- 1. Must be 18 to 79 years of age.
- 1. Must have newly diagnosed multiple myeloma with a history of a minimum of 4 cycles of induction therapy, have received HDT and ASCT within 12 months of the start of induction therapy, and be within 6 months of ASCT on the date of randomization.
- 2. Must have a VGPR or better response assessed per IMWG 2016 criteria at the time of randomization.
- 3. Must have archived bone marrow samples collected before induction treatment (ie, at diagnosis) or before transplant (eg, at the end of induction) or have existing results on the

index MM clone based on Adaptive Biotechnologies' NGS-based MRD assay. Archived bone marrow samples will be used for calibration of myeloma clonal cells to facilitate assessment of the primary end point by NGS. If an existing result on index myeloma clone is available from Adaptive Biotechnologies' NGS-based MRD assay, as part of institutional procedures, an archived bone marrow sample is not required as long as Adaptive Biotechnologies is able to retrieve historical results on the index myeloma clone form the clinical database. Any one of the following archived samples are required:

- a. Greater than 1 mL viable frozen bone marrow aspirated aliquot (preferred) collected in an EDTA tube, frozen, and stored at a temperature of -80°C, or
- b. Non-decalcified diagnostic bone marrow aspirate clot sections (block or slides) for MRD assessment:
- An FFPE block of bone marrow aspirate clot, or slides (preferably 5, if available),
 5 μm each, of non-decalcified bone marrow, or
- ii. Slides (preferably 5, if available), bone marrow aspirate smear,
- iii. Please note, bone marrow core sections are not acceptable samples for analysis.
- iv. In exceptional circumstances when index myeloma clone cannot be identified from the archived bone marrow sample, a post-transplant sample can be used to identify myeloma clone with permission from the Sponsor.

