1.2. Trial Design

This is a Phase 3, randomized, open-label, active-controlled, multicenter study to be conducted at sites in the United States (US) and Canada to primarily evaluate the conversion rate to MRD negativity following 12 months of maintenance treatment with SC daratumumab in combination with lenalidomide relative to treatment with lenalidomide alone in patients with newly diagnosed multiple myeloma who have received at least 4 cycles of induction with or without consolidation, have undergone HDT and ASCT within 12 months of the start of induction, are within 6 months of the ASCT date at the time of randomization, have very good partial response or better at the time of randomization, are MRD positive at the time of screening, and are anti-CD38 treatment naïve.

The study includes a Screening Period; a Maintenance Phase; an End of Treatment (EOT) Visit; and a Follow-up Phase as described below.

- Screening Period: Screening is to be conducted within 60 days prior to randomization; randomization must be within 6 months of the transplant date. Patients must have undergone HDT and ASCT within 12 months of the start of induction therapy.
- Maintenance Phase: Comprised of up to thirty-six, 28-day cycles. Patients will be randomized to receive maintenance treatment with SC daratumumab in combination with lenalidomide or lenalidomide alone. Study treatment will continue until confirmed progressive disease (PD), unacceptable toxicity, withdrawal from study or the end of study maintenance phase.
- EOT Visit: An EOT visit is to be scheduled 30 days (\pm 7 days) after the last dose of study treatment(s) or, if a patient begins new therapy for multiple myeloma, as soon as possible prior to the start of next-line therapy.
- Follow-up Phase: After the EOT visit, patients will continue to be followed until the end of the study. The end of the study is defined as 36 months from the date of randomization of the last patient. If a patient has died, the date and cause of death will be collected and documented in the eCRF.

Planned enrollment includes a total of 214 patients to be randomly allocated in a 1:1 ratio to one of the two treatment arms, with randomization stratified by cytogenetic risk at screening as determined by the investigator (high risk versus standard/unknown risk).

Study evaluations will include evaluation of the following:

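### SAP 5.4.1 assumes every patient is in VGPR at baseline, which contradicts the eligibility criterion and its own rules for prior CR, and leaves the shift-table baseline and the share of new CR unclear

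*SAP*

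**What the plan says.** In the paragraph that defines the CR-or-better and sCR rates, SAP 5.4.1 states: "All subjects are assumed to be VGPR at baseline to enter the study per inclusion criteria". The criterion it appeals to is wider. Protocol 4.1 reads "Must have a VGPR or better response assessed per IMWG 2016 criteria at the time of randomization", and SAP 1.2 describes patients who "have very good partial response or better at the time of randomization". Protocol 3.2.6 expects the benefits to outweigh the risks "even among patients who may achieve a CR or better after transplant", and Protocol 3.2.4 discusses patients in CR who remain MRD positive. Patients in CR therefore belong to the intended population.

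SAP 5.4.1 itself goes on to handle such patients. For duration of CR: "Subjects who achieved CR or sCR prior to randomization will use randomization date as their starting time of CR or sCR". For time to response: "For subjects who achieved CR or sCR prior to randomization, time to CR or better will be set as 0 day".

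The section also plans shift tables: "Shift tables will be provided to summarize the best responses from baseline vs. post-baseline for each treatment group". It does not say whether the baseline category is the assumed VGPR or a recorded response. The sentence just before it concerns investigator-assessed response.

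Under SAP 5.4.2 the CR-or-better and sCR rates are analysed on the full analysis set, in the same way as the primary endpoint. Baseline response is not the stratification factor (SAP 5.2.3), not a subgroup (SAP 2.4, Table 1) and not a listed baseline characteristic (SAP 4.1, Table 3). SAP 5.1.1 treats these endpoints as exploratory.

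**The concern.** Two separate questions arise.

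The first is the rule itself. Applied literally, it misclassifies every patient who enters in CR or sCR. A shift table built on it would present a response that existed before randomization as one that deepened on study.

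The second is what the CR rates mean. A patient in CR at entry who still meets the criteria afterwards counts as achieving CR. The rate therefore mixes retained with newly achieved responses, and no listed table separates them. The analyses touched are the CR-or-better and sCR rates, the CR-or-better forest plot, possibly the shift tables, and the supplementary MRD-negative CR rate in SAP 5.2.3. CR and sCR rates are secondary endpoints in Protocol Table 1, so readers will interpret them even though their tests are exploratory.

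**Working it through.** The documents state no CR rate, baseline CR share or assumed CR effect, so there is no figure to reproduce.

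**Step 1. Compare the rules.**

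| Place | What it implies about baseline CR/sCR |
|---|---|
| Protocol 4.1; SAP 1.2 | Allowed |
| Protocol 3.2.6 | Expected in some patients |
| SAP 5.4.1, response rates | None: everyone is VGPR |
| SAP 5.4.1, duration of CR | Present: clock starts at randomization |
| SAP 5.4.1, time to CR | Present: time is 0 days |

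If the third row were true, the last two would apply to nobody. The SAP contradicts itself and does not carry the assumption through.

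**Step 2. Shift tables under each reading.** With the assumed category, there is one baseline row, and a patient in CR before and after appears as VGPR to CR. With the recorded category, there are rows for VGPR, CR and sCR, and the same patient appears as CR to CR. The text does not choose between them.

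**Step 3. CR-or-better rate on the full analysis set.** Let b be the share in CR at entry (equal in both arms under randomization, apart from chance), s the proportion of those counted again as CR after randomization, and p the conversion rate among the rest:

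rate = b × s + (1 − b) × p

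With s = 1 in both arms:

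- rate = b + (1 − b) × p
- rise over p = b × (1 − p)
- difference between arms = (1 − b) × (p for DR − p for R)

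All inputs are assumptions: b from 20% to 50%, and p of 20% (R) and 40% (DR). The two conversion rates are borrowed from the MRD assumption in SAP 1.4. They are not CR figures.

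| b | R rate | DR rate | Difference | Odds ratio | Share of counted CRs present at entry, R / DR |
|---|---|---|---|---|---|
| 0% | 20% | 40% | 20 points | 2.67 | 0% / 0% |
| 20% | 36% | 52% | 16 points | 1.93 | 56% / 38% |
| 30% | 44% | 58% | 14 points | 1.76 | 68% / 52% |
| 40% | 52% | 64% | 12 points | 1.64 | 77% / 62% |
| 50% | 60% | 70% | 10 points | 1.56 | 83% / 71% |

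Example at b = 30%: R is 0.30 + 0.70 × 0.20 = 0.44 and DR is 0.30 + 0.70 × 0.40 = 0.58. The rises are 24 and 18 points. The arm with the lower conversion rate gains more, and that narrows the gap.

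At b = 20%, 56% of counted CRs in the R arm predate randomization. Under the 0-day rule that arm's median time to CR would be 0 days, in a plan that also describes everyone as VGPR at baseline.

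**Step 4. Are baseline data available?** The Time and Event Schedule (Part 1) marks investigator IMWG response, serum and urine immunofixation, and FLC at screening and C1D1, and marrow morphology and clonality at screening. Protocol Table 7 defines CR by negative immunofixation, absence of soft tissue plasmacytomas and marrow plasma cells below 5%. None of these needs a pre-induction value.

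**The case against.** The strongest reply is that the rates would be the same without the sentence. The endpoint counts anyone who meets CR during or after treatment, so a retained CR counts by definition. A reader might infer that the VGPR assumption causes baseline CR to be credited to treatment. The documents do not support that, because deleting the sentence changes no CR or sCR rate. This part of the reply stands.

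A reader might also infer that the shift tables are wrong. That is not shown. They follow the sentence on investigator-assessed response, which is recorded at screening and C1D1, and a shift table has little purpose if baseline does not vary. Recorded response is a plausible reading, but the text does not state it, and the only baseline rule in the paragraph is the assumed VGPR.

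A third possible inference is that counting baseline CR favours daratumumab, or raises both arms equally. Neither follows. Both arms are raised, and in the illustration the lenalidomide arm is raised more. Baseline response is not stratified, so chance imbalance could go either way.

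The reply is also right that a full-analysis-set comparison is a valid randomized comparison, and that the illustration rests on inputs the documents do not give. It is right too that not every baseline category can be derived by algorithm. The 90%-reduction route to VGPR needs an earlier M-protein value that the schedule does not list, marrow is not scheduled at C1D1, and local marrow results may substitute at screening. The investigator's recorded category should therefore be the main source.

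None of this rescues the sentence itself, which misstates the criterion it cites.

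**Conclusion.** The concern holds as a definitional error and an internal contradiction in SAP 5.4.1. Every patient in CR or sCR at entry would be misclassified if the rule were applied. Shift tables built on it would show retained CR as improvement, and if it is not applied, their baseline source is unstated.

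The mixing of retained and new CR is a separate matter that comes from the endpoint definition. It raises both arms' rates and tends to dilute the difference. Its size cannot be determined from the documents. The shrinkage from 20 points to between 16 and 10 is an illustration that assumes 20% to 50% in CR at entry, equal shares in both arms, all of them retained, and 20% versus 40% conversion among the rest. If retention differed by arm, the term b × (s for DR − s for R) would add to or subtract from the difference.

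The primary MRD conversion endpoint and PFS do not use the baseline response category and are unaffected. The CR and sCR tests are exploratory. The change should be made, but it does not threaten the trial's main conclusions.

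**What to change.** 1. Replace the sentence in SAP 5.4.1 with a definition of baseline response (VGPR, CR or sCR). Use the investigator's recorded assessment at screening/C1D1, supported by the central immunofixation and FLC results and the screening marrow. Align the timing with the baseline definition in SAP 2.6, and check it against the two prior-CR rules in the same section so that all three use one classification.
2. Add baseline response to the baseline characteristics in SAP Table 3.
3. Name it as the baseline source for the shift tables.
4. Keep the full-analysis-set CR-or-better and sCR rates. Beside them, report new CR-or-better among patients not in CR or sCR at baseline, and new sCR among patients not in sCR at baseline. Both subsets are defined before randomized treatment starts, so the arms remain comparable apart from chance imbalance.

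The cost is SAP wording and one added table. The assessments are already scheduled, so no new data collection is needed.
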